9.2 Comparative-effectiveness analysis

Prior to analyses, we will produce data summaries to assess data quality, examine data distribution, and randomization success. All analyses will be performed using intention-to-treat. Data can be missing for any day if the participant did not use the activity tracking device or did not upload data. For the main analysis we will use multiple imputation for step values that are missing or less than 1000 steps. We will perform five sets of imputations and results will be combined using Rubin's standard rules.²⁸ We will perform sensitivity analyses to assess the robustness of the findings using only collected data with and without step values less than 1000 steps. Since minutes of MVPA are derived from step counts, this process should address missing data for MVPA as well.

Similar to prior work,¹² the primary analysis will fit linear mixed effect regression models to evaluate changes in physical activity outcomes measures (primary and secondary outcomes) adjusting for each participant's baseline measure, time using calendar month fixed effects, participant random effects, and accounting for repeated measures. Secondary analyses will fit linear mixed effect regression models adjusted for other variables of interest such as participant demographic characteristics and cardiovascular history. Exploratory analyses will fit logistic mixed effect regression models to evaluate the proportion of weeks that CDC guidelines for physical activity were achieved.

We will perform subgroup analyses using available participant sociodemographic characteristics including age, sex, race/ethnicity, education, and income level. We will also conduct subgroup analyses using differences in baseline measures such as baseline step count and atherosclerotic cardiovascular disease (ASCVD) 10-year risk score. If differences in outcomes exist, we will fit a fully adjusted model that includes these covariates and interaction terms with the treatment arms to evaluate for statistical significance.

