9.1 Power and sample size

Physical activity has been demonstrated to have a direct dose relationship with reduction in the risk of cardiovascular disease and events, with even small increases significantly lowering risk.^{6,22-25} We use 1000 steps as our threshold for powering statistical significance, which for the average person is about half a mile and takes about 10 minutes of MVPA.²⁶ Based on our prior work,¹⁰⁻¹⁴ we estimate a standard deviation in the primary outcome of 2500 steps. This study has been powered for six comparisons

between arms using a common cutoff for the test statistics that ensures the familywise error rate is at most 0.05. This is the approach suggested in Follmann et al.²⁷ and it generalized Tukey's Honest Significant Differences approach for an unbalanced design. We estimate that a sample of 1050 participants allocated in a 1:2:2:2 distribution (150 in control and 300 in each intervention arm), will ensure 93% power to detect a 1000 step difference between each intervention arm and control, with a standard deviation of 2500 steps and an 8-minute difference in MVPA assuming a standard deviation of 20 minutes. This calculation assumes a 10% dropout rate. We estimate that we will have at least 85% power to detect a 750-step difference with a standard deviation of 2500 steps and a 6-minute difference in MVPA with a standard deviation of 20 minutes.

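### Optional improvement: five imputations in the main analysis are valid but add avoidable Monte Carlo noise, and 50 would remove most of it for computing time alone

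*Combined protocol and SAP*

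**What the plan says.** Section 9.2 of the combined protocol and SAP sets the missing-data method for the main analysis: "we will use multiple imputation for step values that are missing or less than 1000 steps". It then fixes the number: "We will perform five sets of imputations and results will be combined using" Rubin's rules. It gives no reason for five, no expected share of missing days, no FMI and no check on Monte Carlo error. The planned sensitivity analyses work "using only collected data with and without step values less than 1000 steps", so they involve no imputation.

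Section 9.1 powers the trial for six comparisons "between arms using a common cutoff for the test statistics that ensures the familywise error rate is at most 0.05". It claims 93% power for 1000 steps between each intervention arm and control, and "at least 85% power to detect a 750-step difference with a standard deviation of 2500 steps". On attrition it says "This calculation assumes a 10% dropout rate". Neither section says how the common cutoff is to be applied to estimates pooled by Rubin's rules, which carry their own degrees of freedom.

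**The concern.** With a finite number of imputations m, the pooled estimate and its estimated variance both depend on the random seed. With m = 5, two correct runs on the same data can fall on opposite sides of the significance cutoff. All six pairwise conclusions come from this one imputed analysis. The small m also costs some power, because the pooled variance is larger and, if Rubin's t reference is used, the critical value is higher. How much this matters depends on how much information is missing, so the check has to cover a range.

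**Working it through.** **Inputs.** From Section 9.1: SD 2500, arms of 150/300/300/300, familywise error 0.05 over six comparisons, 10% dropout. From Section 9.2: m = 5. Assumed, because the plan is silent: FMI of 0.02 to 0.30, equal in all arms. The 750-step difference is taken as intervention against intervention, because Section 9.1 does not name the comparison.

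**The plan's own figures.** The simulated common cutoff for all pairs is 2.566.
- 1000 steps v control: SE = 2500 × √(1/150 + 1/300) = 250.0; 1000/250 − 2.566 = 1.434; power 92.4% (stated 93%).
- 750 steps between interventions: SE = 2500 × √(2/300) = 204.1; 750/204.1 − 2.566 = 1.108; power 86.6% (stated at least 85%).

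Both reproduce with 150 and 300 as the analysed numbers.

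**Effect of missing information alone.** With unlimited imputations the variance is the complete-data variance divided by (1 − FMI). At FMI 0.10 this equals analysing 135 v 270: SE = 250/√0.9 = 263.5 and power 89.1%. The 750-step power is 82.1%. These are the ceilings for any m at that FMI.

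**Effect of m (FMI 0.10).**
- Monte Carlo SE = SE × √(FMI/m). For m = 5: 263.5 × √0.02 = 37 steps. For m = 50: 263.5 × √0.002 = 12 steps. The ratio is √10 = 3.2.
- Degrees of freedom = (m − 1)(1 + 1/r)², with r = (1 + 1/m) × FMI/(1 − FMI). For m = 5: r = 1.2 × 0.1/0.9 = 0.133, so df = 4 × 8.5² = 289 and the critical value rises from 2.566 to 2.582. For m = 50, df is 4729 and the critical value is 2.567.
- At FMI 0.30 and m = 5, df is only 35 and the critical value 2.713. The choice of reference therefore matters there. At FMI 0.02 it does not (df about 7,000).

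**Simulation.** For each dataset, m imputed arm means were drawn and pooled with T = U + (1 + 1/m)B. Two independent sets of imputations per dataset gave the seed disagreement. The t-reference runs used 200,000 datasets for m = 5 and 60,000 for m = 50. The common-cutoff runs used 100,000 and 30,000. Entries are m = 5 / m = 50; a dash means not computed.

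| FMI | Reference | Power, 1000 v control (%) | Power, 750 between interventions (%) | Two seeds disagree: 1000; 750 (%) |
|---|---|---|---|---|
| 0.02 | either | differ by about 0.2 or less | differ by about 0.2 or less | 1.2 / 0.3; 1.7 / 0.5 |
| 0.05 | t | 90.4 / 90.9 | 84.0 / 84.3 | 2.2 / 0.6; 3.2 / 1.0 |
| 0.10 | t | 87.8 / 89.0 | 80.5 / 82.1 | 4.4 / 1.1; 6.0 / 1.5 |
| 0.10 | common cutoff | 88.4 / 89.0 | 81.4 / 82.2 | 3.9 / –; 5.2 / – |
| 0.30 | t | 69.3 / 77.5 | 60.4 / 68.9 | – |
| 0.30 | common cutoff | 74.9 / 78.1 | 66.5 / 69.3 | – |

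A repeat of the common-cutoff run put the loss at FMI 0.10 at about 0.7 to 1 point.

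**Familywise error with m = 5.** At FMI 0.10 it is about 5.0% (t) to 5.3% (common cutoff). At FMI 0.30 it is about 5.5% to 6.6%. With m = 50 it returns to about 5%.

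**What one re-run can do.** For a result exactly at the cutoff (p = 0.0103, FMI 0.10), the 5th to 95th percentile of p under a new seed is 0.005 to 0.026 with m = 5 and 0.008 to 0.013 with m = 50.

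**Twenty imputations (FMI 0.10, t reference).** Power is 88.9% and 81.8%, close to m = 50. Seed disagreement is 1.8% and 2.5%, so 1.8/4.4 = 41% and 2.5/6.0 = 42% of the m = 5 disagreement remains.

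**The case against.** The strongest reply is that five imputations are valid, nothing in the plan conflicts with them, and preferring 50 is a matter of judgement. This stands, and it is why the point is optional. Fifty is also not the only defensible number: on power alone, 20 does nearly as well.

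Second, FMI 0.10 is probably high for the stated dropout. It needs every dropout to contribute nothing after baseline. Scattered missing days add little, because the outcome averages about 365 − 56 = 309 days. With independent days, a within-person daily SD of 4000 and 40% of days missing (all assumed), the added variance is 4000² × (1/185 − 1/309), about 34,700. Against 2500² = 6,250,000 that is under 0.01. Long spells of non-wear and imputed values below 1000 would add more, but the plan gives no rates. This stands too, so the low-FMI rows belong beside the 0.10 rows.

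Third, the planned sensitivity analyses on collected data need no seed, so a borderline result would be seen beside a seed-free one. That helps interpretation, but it does not reduce the noise in the main analysis. Fixing the seed in advance makes one run repeatable but leaves the answer dependent on an arbitrary seed.

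A reader might infer a loss of 8 to 9 points of power. That needs both FMI 0.30 and Rubin's t reference, and the documents give neither. With one common cutoff the loss at FMI 0.30 is about 3 points.

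**Conclusion.** The point holds as an optional improvement. Five imputations are usable, but they leave avoidable seed-dependence in six conclusions and cost a little power. At FMI 0.10 the power cost is about 1 to 2 points (t reference) or 0.7 to 1 point (common cutoff), and seed disagreement is roughly four times as frequent as with 50. At FMI 0.02 to 0.05 both effects are small. Confidence is high that five is what the plan fixes and that 50 is quieter. It is medium for the magnitudes, which rest on an assumed FMI and an unstated reference distribution.

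Three stronger readings are not supported. First, the plan is not invalid: at FMI 0.10 familywise error stays near 5%, and the excess at FMI 0.30 depends on a level of missing information the documents do not state. Second, the fall from the stated 93% and 85% to about 89% and 82% is not caused by five imputations. It comes from the assumed missing information and is there with 50 as well. Third, more imputations do not recover what dropout loses, nor do they repair a poor imputation model.

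**What to change.** In Section 9.2, change the number of imputations for the main analysis from five to 50. Keep Rubin's rules and the planned sensitivity analyses as they are.

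The cost is about ten times the computing time and one changed number in the text. Participants and data collection are unaffected. Familywise error is not made worse: where five imputations push it above 5%, 50 bring it back to about 5%. If computing time is a real constraint, 20 would recover most of the power but leave about 40% of the seed disagreement.

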5.1 Design

This is a four-arm, randomized, controlled trial to test the effectiveness of gamification, financial incentives, or both to increase physical activity among individuals with a 10-year ASCVD risk score of 7.5% or higher. There will be a 2-week run-in period to obtain baseline measures of physical activity, followed by a 12-month intervention period and then a 6-month follow-up period.

Participants will use the Penn Way to Health research technology platform to provide informed consent and complete eligibility surveys. Eligible patients will be mailed a wearable activity tracker that captures data on daily steps counts and minutes of MVPA. They will be asked to use the device for two weeks to get accustomed to it. During this period, we will use a protocol from prior work to estimate a baseline step count using the second week of data. The first week of data will be ignored to diminish the tendency for use of devices in week 1 of receiving a new device to be significantly higher than what might be observed at steady state. To prevent risk of mismeasurement, we will ignore any daily values less than 1000 steps because evidence indicates these values are unlikely to represent capture of actual activity.^{15,16} At least four days of data must be available during that second week to estimate baseline measures; otherwise the period will be extended. In prior work, we typically have 6 to 7 days of data from more than 90% of participants.¹² Participants who do not complete this run-in phase will not be randomized into the trial. Participants will also complete a series of validated surveys including risk preferences (DOSPERT),¹⁷ social support (Medical Outcomes Study),¹⁸ personality (Big Five) and health-related quality of life (EQ-5D).¹⁹⁻²¹ See table in Section 8.2 for full list of surveys and timing

--Goal Setting--

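### Imputing daily steps does not by itself supply missing MVPA minutes; section 9.2 should state that MVPA is imputed as well, and how

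*Combined protocol and SAP*

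**What the plan says.** Section 9.2 (Comparative-effectiveness analysis) recognises day-level gaps: "Data can be missing for any day if the participant did not use the activity tracking device or did not upload data". The remedy in its principal analysis names steps alone: "we will use multiple imputation for step values that are missing or less than 1000 steps", with five imputations combined by Rubin's rules. The paragraph ends with the only statement on MVPA: "Since minutes of MVPA are derived from step counts, this process should address missing data for MVPA as well". Sensitivity analyses are planned "using only collected data with and without step values less than 1000 steps".

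The 150-minute outcome of section 3.3 is analysed with logistic mixed models "to evaluate the proportion of weeks that CDC guidelines for physical activity were achieved".

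Section 5.1 (Design) describes a tracker that records both daily steps and MVPA minutes. For the run-in it says "we will ignore any daily values less than 1000 steps because evidence indicates these values are unlikely to represent capture of actual activity", and it sets a minimum: "At least four days of data must be available during that second week to estimate baseline measures; otherwise the period will be extended". From earlier studies it reports that "we typically have 6 to 7 days of data from more than 90% of participants".

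The documents contain no imputation model that includes MVPA, no function taking an imputed step count to MVPA minutes, and no rule for scoring a week with missing days against 150 minutes.

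**The concern.** The MVPA sentence needs step imputation to carry over to MVPA. It would do so if a daily step total determined the minutes, but it does not: the same total can come from slow walking spread over the day or from a few brisk bouts. This holds even if the device works out MVPA from step data within the day, because what is imputed is only the daily total.

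A second gap follows. Where a recorded step value under 1000 is replaced, the plan does not say what happens to the MVPA recorded that day. Left in place, a low MVPA value from a day judged not to be real capture sits beside an imputed, higher step count.

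The outcomes at stake are change in mean daily MVPA to the intervention period and to follow-up (section 3.2), the weekly 150-minute outcome (section 3.3) and MVPA as an effect measure in section 9.3. An analyst could impute MVPA, convert it from imputed steps, or leave it missing. These choices can give different results from the same data, and the plan does not settle between them.

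**Working it through.** **1. What is imputed and what is needed**

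| Item | Section | Content |
|---|---|---|
| Variable imputed | 9.2 | Daily steps, if missing or under 1000 |
| Source of MVPA | 5.1 | Recorded by the tracker alongside steps |
| Handling of missing MVPA | 9.2 | Expected to follow from step imputation |
| MVPA recorded on a sub-1000-step day | none | Not stated |
| Secondary outcomes using MVPA | 3.2 | 2 of 3 |
| Weekly outcome | 3.3, 9.2 | At least 150 minutes; no rule for missing days |

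**2. Could a figure in the plan serve as a conversion?** Section 9.1 has the only figures linking steps and minutes.
- Rationale for the threshold: about 10 minutes per 1000 steps.
- Power inputs: 8 minutes beside 1000 steps, 8/1000 = 0.008; 6 minutes beside 750 steps, 6/750 = 0.008; ratio of SDs, 20/2500 = 0.008. Each equals 8 minutes per 1000 steps.
- As conversions they differ by 10/8 = 1.25, or 25%. A 6000-step day would get 60 or 48 minutes, as if every step were moderate to vigorous.

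Section 9.1 offers neither as a conversion, and neither would be a sensible intensity rule.

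**3. Where incomplete weeks remain.** If MVPA is imputed on every missing day, all post-baseline weeks in the main analysis have seven days. Incomplete weeks then remain in two places: baseline weeks with 4 to 6 usable days, which section 5.1 accepts, and the sensitivity analyses on collected data.

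**4. How much the scoring rule could matter there (hypothetical).** A full week needs 150/7 = 21.4 min/day. With k recorded days, summing needs a mean of 150/k on those days, while mean times 7 still needs 21.4.

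| k | 150/k (min/day) | Ratio 7/k | Increase |
|---|---|---|---|
| 6 | 25.0 | 1.17 | 17% |
| 5 | 30.0 | 1.40 | 40% |
| 4 | 37.5 | 1.75 | 75% |

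For example, 25 min/day on five recorded days gives 25 × 7 = 175 (met) when prorated and 25 × 5 = 125 (not met) when summed. The plan proposes neither rule; the table shows only why one should be named.

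**5. Share of complete weeks in observed data (assumed rates).** The documents give no missingness rate for the intervention or follow-up. If each day is missing independently with probability m, the share of weeks with all seven days is (1 − m)^7: 0.9^7 = 48%, 0.8^7 = 21%, 0.7^7 = 8%. In a simulation with assumed daily MVPA (mean 20 minutes, between-person and within-person SD 15 each, negative values set to zero), 48% of full weeks reached 150 minutes. Summing recorded minutes lowered this to 41%, 33% and 26% at the three rates; prorating kept it near 48%. These are illustrations, not estimates for this trial.

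**The case against.** The strongest reply is that the MVPA sentence means the whole procedure, imputation and both sensitivity analyses, is to be applied to MVPA as well. The wording allows this. On that reading the plan has the right intent and lacks only the mechanics, including the treatment of sub-1000-step days, which would follow by analogy. This stands as a possible reading, but the sentence justifies itself by saying that MVPA comes from steps, which points towards derivation from imputed steps. The two readings lead to different analyses.

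Several further points stand:
- The imputation model for steps is not stated either, so the lack of a model is not peculiar to MVPA. What is peculiar is the premise offered in its place.
- The four-day rule in section 5.1 speaks of baseline measures in the plural and reasonably covers mean baseline MVPA. It does not say how a 4- to 6-day week is scored against 150 minutes.
- The most exposed outcome, weekly status, is exploratory.

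A reader might go further and infer that the MVPA comparisons will be biased, that incomplete weeks undermine the main analysis throughout, or that the 17%, 40% and 75% shifts measure the error. The documents support none of these. They give no rate of missing or sub-1000-step days after baseline, no difference between arms and no MVPA distribution. Full imputation of MVPA removes incomplete post-baseline weeks from the main analysis. The percentages compare two rules that the plan does not propose, and at baseline most weeks should be nearly complete if the earlier studies are a guide.

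**Conclusion.** The point holds as a flaw in one sentence of the missing-data plan. Imputed step totals do not determine MVPA minutes, and taken literally the rule neither supplies valid MVPA on missing days nor removes recorded MVPA from days regarded as non-capture. If the same imputation was meant for MVPA, it has to be stated.

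The consequence is limited. The primary step outcome is untouched. For mean MVPA, a mixed model on observed valid days would be valid if days are missing at random given the terms in the model, so bias is not a foregone conclusion; its size and direction are unknown. Joint imputation rests on a similar assumption and would not by itself protect against wear that depends on unrecorded activity. The weekly threshold outcome is more sensitive, but a separate scoring gap remains only at baseline and in the collected-data analyses.

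Severity is minor to moderate: high confidence in the gap, none in any particular amount of bias.

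**What to change.** Replace the MVPA sentence in section 9.2 with wording such as:

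> Daily MVPA in the intervention and follow-up periods will be set to missing on days when steps are missing or below 1000, and multiply imputed jointly with daily steps. The model will include arm, baseline steps, baseline MVPA, calendar month and a participant effect, and will use a method that respects non-negative minutes. Weekly 150-minute status will be derived within each completed data set.

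Then add two clarifications:
- Baseline weeks with 4 to 6 usable days, and incomplete weeks in the sensitivity analyses on collected data, are scored as mean daily MVPA times 7, not by summing recorded minutes. This puts baseline on the same seven-day scale as the completed trial weeks. Whether trial weeks need a minimum number of recorded days is for the sponsor to decide; the documents set one only for baseline.
- Both collected-data sensitivity analyses apply to MVPA, with sub-1000-step days kept in one and dropped in the other. Because the baseline excludes such days, the analysis that keeps them should note this difference.

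The cost is SAP wording and a somewhat larger imputation model, whose specification is needed for steps in any case. No new data and no change to trial conduct are required.

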3.2 Secondary outcomes

Secondary outcomes include change in mean daily steps from baseline to the post-intervention follow-up period, change in mean daily minutes of moderate-to-vigorous physical activity (MVPA) from baseline to the intervention period, and change in mean daily minutes of MVPA from baseline to the post-intervention follow-up period.

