Once baseline measures have been established, participants will be contacted to choose their goals using an approach we have found to work well in previous studies. They will be given their baseline step count and asked to select a step goal increase of 33%, 40%, 50% or choose a custom goal as long as it is at least 1500 steps greater than baseline. We have used this approach in the past because it gives participants the options of setting their own goal but also steers people to choose one of the options provided, any of which would be terrific from the standpoint of increasing physical activity. Leaving it completely open-ended risks having participants either pick goals that are ‘too easy’ or not likely to be attainable. In prior work, we find that on average participants chose ambitious goals and more than half selected a 50% step increase.

--Randomization—

Participants that have established baseline measures and finished goal selection will be randomly assigned to control or one of the three interventions using a 1:2:2:2 allocation and stratifying on baseline step count (< 4000 steps, 4000 – 7000 steps, > 7000 steps) using an electronic number generator through the Way to Health research technology platform. We do this because it preferentially increases power for comparison between the different intervention arms, as the differences between intervention arms are likely to be smaller than the difference between the intervention arms and control.

--Study Arms—

All participants will be asked to use the wearable device during the day and at night to measure activity. Each participant will primarily receive study communications by text message. Interventions by study arm will vary as follows:

--Arm 1: Control—

During the intervention and follow-up periods, participants in this arm will receive a daily text message stating whether or not they achieved their step goal on the prior day.

--Arm 2: Gamification intervention—

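### Section 9.2 does not commit to baseline step count, the randomisation stratifier, in the MVPA models or the CDC-guideline model; naming it is a small, nearly free gain in precision

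*Combined protocol and SAP*

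**What the plan says.** Section 5.1 (Randomization) allocates 1:2:2:2, "stratifying on baseline step count" in three bands: below 4000, 4000 to 7000, and above 7000 steps. Section 5.6 excludes anyone with a baseline of 7,500 steps or more.

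Section 9.2 gives one covariate list for the linear mixed models of the primary and secondary outcomes, which adjust for the participant's "baseline measure, time using calendar month fixed effects, participant random effects, and accounting for repeated measures". The secondary outcomes in section 3.2 include "change in mean daily minutes of moderate-to-vigorous physical activity (MVPA) from baseline to the intervention period" and the corresponding change to the follow-up period.

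For the guideline outcome, section 9.2 says: "Exploratory analyses will fit logistic mixed effect regression models to evaluate the proportion of weeks that CDC guidelines for physical activity were achieved". It lists no covariates for that model.

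Two other sentences in section 9.2 come close to the stratifier without settling the matter. Further models are to be "adjusted for other variables of interest such as participant demographic characteristics and cardiovascular history", which does not name baseline steps. Baseline steps do appear under "subgroup analyses using differences in baseline measures such as baseline step count", but there they enter a model with interaction terms only if outcome differences are seen.

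**The concern.** When randomisation is balanced on a prognostic factor, the estimated treatment difference is already protected against chance imbalance in that factor. If the model then leaves the factor out, its residual variance still contains the variation between strata, and the reported standard error is at least as large as it needs to be. The usual practice is to analyse as randomised.

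Here the step outcomes meet that standard because their own baseline is the stratifier. The two MVPA outcomes and the guideline outcome do so only if someone chooses to add baseline steps. At stake is some precision for two of the three secondary outcomes and for the exploratory outcome, plus a covariate choice left open until analysis.

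**Working it through.** **1. Models against the stratifier**

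| Outcome | Covariates stated in 9.2 | Baseline steps committed to? |
|---|---|---|
| Steps, intervention period (primary) and follow-up (secondary) | participant's baseline value, calendar month, random effect | Yes, it is the baseline value |
| MVPA, intervention period and follow-up (secondary) | same list | Not clearly; the natural reading is baseline MVPA |
| CDC guideline weeks (exploratory) | none listed | No |

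**2. The plan's own figure**

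Section 9.1 states 93% power for 8 minutes of MVPA (SD 20), intervention (300) versus control (150), with one common cutoff for six comparisons. Simulating that cutoff for 1:2:2:2 gives 2.566.

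- SE = 20 × √(1/150 + 1/300) = 2.0 minutes
- Power = Φ(8/2.0 − 2.566) = Φ(1.434) = 92.4%

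This agrees with 93% if all 1050 are analysed. With the stated 10% dropout taken off (135 versus 270) it is 89.0%. That is a separate matter; 92.4% is used here only as a starting point.

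**3. MVPA: effect of adding baseline steps**

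Let p be the partial R-squared, the share of residual variance that baseline steps remove beyond baseline MVPA. The SE is multiplied by √(1 − p), and power becomes Φ(4.0/√(1 − p) − 2.566).

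| Assumed p | SE reduction | Power, 8 min, 150 vs 300 |
|---|---|---|
| 0 | 0% | 92.4% |
| 0.02 | 1.0% | 93.0% |
| 0.05 | 2.5% | 93.8% |
| 0.10 | 5.1% | 95.1% |

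**4. Which p is plausible?**

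Let a be the correlation of follow-up MVPA with baseline MVPA, b its correlation with baseline steps, and c the correlation between the two baselines. The documents give none of these. Then R² = (a² + b² − 2abc)/(1 − c²) and p = (R² − a²)/(1 − a²).

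| a, b | c = 0.6 | c = 0.8 | c = 0.9 |
|---|---|---|---|
| 0.5, 0.45 | 4.7% | 0.9% | 0.0% |
| 0.4, 0.40 | 4.8% | 2.1% | 1.0% |

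Example: (0.25 + 0.2025 − 0.27)/0.64 = 0.285, and (0.285 − 0.25)/0.75 = 4.7%.

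In these examples p shrinks quickly as the two baselines become more alike. In the combinations tried, p of 0.07 or more arose only where baseline steps predicted follow-up MVPA better than baseline MVPA did. One such case is a = 0.4, b = 0.45, c = 0.6, which gives 8.2%.

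**5. CDC-guideline model**

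To size this, 150 versus 300 participants were simulated with 44 weeks each (12 months less the 8-week ramp-up, an assumption for this outcome). Other assumptions were a between-participant SD of 2.0 on the logit scale, an intercept of −1.5 and a treatment log odds ratio of 0.9. Participant-level empirical logits were analysed with and without baseline steps and with no other covariate. This approximates the random-intercept logistic model.

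| Share of between-participant variance explained by baseline steps (assumed) | SE without | SE with | Reduction |
|---|---|---|---|
| 0% | 0.193 | 0.193 | 0% |
| 5% | 0.193 | 0.189 | 2% |
| 10% | 0.193 | 0.184 | 5% |
| 20% | 0.193 | 0.174 | 10% |
| 30% | 0.193 | 0.164 | 15% |

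As a check, if all the variance were between participants the 30% row would give 1 − √0.70 = 16%; week-to-week noise brings it to 15%. The estimated treatment effect was about 0.83 in every row, with or without the covariate.

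**The case against.** The text is ambiguous or silent; it does not exclude the factor. A reader might infer that the MVPA and guideline models have been specified without baseline steps. The documents do not support that. The covariate list does not say which baseline measure is meant for MVPA. The guideline sentence gives a model family and an outcome, not a complete model, and section 3.3 defines that outcome as a change from baseline, so some baseline information is presumably intended. This stands, and the point is limited to a missing commitment.

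The MVPA gain may be close to nothing. Section 9.2 justifies its missing-data approach by saying "Since minutes of MVPA are derived from step counts". If so, baseline MVPA and baseline steps overlap heavily, and the right-hand columns in step 4 are the more relevant ones. This also stands.

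Nor do baseline steps repair a short baseline window, since both measures come from the same second run-in week with the same four-day minimum. That is fair for MVPA. It has less force for the guideline outcome, whose own baseline is a single yes/no week, whereas step count is continuous and keeps information that the dichotomy discards.

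What the objection does not remove is that the design balances on a factor that three analyses do not promise to use.

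**Conclusion.** The point holds as a modest improvement in efficiency for two secondary outcomes and one exploratory outcome. For MVPA the standard error would fall by about 0 to 5% (assumed partial R-squared 0 to 0.10), probably towards zero. For the guideline model it would fall by about 0 to 15% (assumed share 0 to 30%, nothing else adjusted for). If guideline status at baseline is also included, the part due to steps would be expected to be smaller. These ranges rest on assumed correlations and on an approximation to the logistic mixed model.

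Three stronger readings are not supported:

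- **Bias, or a weakness in the primary result.** Randomisation protects the comparison, and both step outcomes already adjust for baseline steps.
- **Tests of a known size below 5%.** Any such effect would be conservative, but it depends on what the three bands, not continuous steps, explain beyond the covariates already in the model. The documents do not give that, and the cutoff described in section 9.1 is a familywise one of about 2.57, not 1.96.
- **A definite gain in power.** Any single figure depends on the correlation between baseline MVPA and baseline steps, which is not reported.

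**What to change.** Add to section 9.2, before comparative data are seen, a sentence to this effect: *All primary, secondary and exploratory models, including the logistic mixed models, will include baseline step count as a continuous fixed effect, in addition to the baseline value of the outcome analysed: baseline mean daily MVPA for the MVPA models, and baseline-week MVPA or guideline status for the guideline models.* For the step outcomes the two terms are the same, so nothing changes there. The sponsor should choose one of the two baseline options for the guideline models in advance.

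Continuous steps are preferable to the strata. With baselines of 7,500 or more excluded, the top band covers only about 7,001 to 7,499 steps, so the bands are a coarse and uneven summary.

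The cost is one sentence. Baseline steps are already collected for every randomised participant. The downside is negligible: the odds ratio from the logistic model is conditional on its covariates, so the list must be fixed in advance and reported with the result.
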